6.2. Statistical Analysis Plan

6.2.1 General Methodology

For baseline demographics and subject characteristics, continuous measures will be summarized as mean, standard deviation, median, minimum and maximum. Categorical data will be summarized as frequencies and percentages for each data category. As appropriate, characteristics of affected segments may be similarly summarized.

For segment specific efficacy endpoints of interest, the analysis unit will be treated segment as opposed to subject. That is, assuming no missing data, subjects with bilateral DVTs will have two segments for analysis. Efficacy results will be summarized for the Efficacy Segment Set at each measurement time point. For changes from baseline at follow-up time points, continuous measures will be summarized as mean, standard deviation, median, minimum, maximum. Categorical outcomes will be summarized in two-way tables. All statistical analyses will take into account the repeated measures nature of multiple segments per subject. With subject as a random effect, the SAS GLIMMIX procedure will generally be used to evaluate the statistical significance for changes from baseline.

Analysis for subject specific efficacy measures such as SF-36 will be performed on the Evaluable Subject Set with subject as the analysis unit. Statistical significance for changes from baseline will be assessed by t-test or a nonparametric test appropriate for the data distribution.

Further analysis details will be described in the Statistical Analysis Plan.

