3.2.1 Secondary Clinical Efficacy Endpoints

1. Occlusive material burden using the Venous Volumetric Index (VVI) Score¹¹, measured at Baseline and Post-EkoSonic® Study Treatment Procedure, both as a continuous measure and as a binary variable for achievement of a ≥ 5 point reduction from Baseline to Post-Procedure.
2. Change in Villalta score from Baseline to 90 days, 180 days, and 365 days Post-EkoSonic® Study Treatment Procedure, both as a continuous measure and as a binary variable for having achieved a ≥ 4 point reduction from Baseline.
3. Absence of re-occlusion at 365 days of the treated segment, as documented by duplex imaging.
4. Change in SF-36 Quality of Life (QoL) and Physical Component Summary (PCS), CEAP classification, VEINES-QOL, and VCSS from Baseline to 30, 90, 180 and 365 days Post-EkoSonic® Study Treatment Procedure.
5. Symptomatic PTS-induced admission to emergency room or unplanned visit to physician office or hospitalization from Post-EkoSonic® Study Treatment Procedure up to 365 days thereafter
6. Time from starting initial thrombolytic infusion to discharge from hospital

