4.5 Subject Withdrawal

Subjects may withdraw from participation at any time during the clinical study. All data collected prior to withdrawal shall remain part of the study. Every effort shall be made to encourage the subject to remain in the trial. If the subject declines, determine and document the reason for withdrawal.

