6.0 STATISTICAL ANALYSIS

6.1. Analysis Subject Sets, Evaluable Subjects and Missing Data Handling Convention

Efficacy Evaluable Segments are defined as DVT segments from enrolled subjects which: (a) were successfully crossed and received EkoSonic® Treatment, and (b) had Villalta scores available at both Baseline and 30 days Post-EkoSonic® Treatment visit. The **Efficacy Segment Set** includes all efficacy evaluable segments and will be used for all segment specific efficacy analyses. A treated segment that received a revascularization procedure within 30 days Post-EkoSonic® Treatment will be regarded as a failure for the primary efficacy endpoint, i.e. without a ≥ 4 -point reduction in Villalta score from Baseline to 30 days Post-EkoSonic® Treatment.

Efficacy Evaluable Subjects are defined as enrolled subjects for whom at least one affected segment: (a) was successfully crossed and received EkoSonic® Treatment, and (b) had Villalta scores available at both Baseline and 30 days Post-EkoSonic® Treatment visit. The **Efficacy Subject Set** includes all efficacy evaluable subjects and will be used for all subject specific efficacy analyses such as for quality of life measures.

Safety Subject Set

Safety evaluable subjects are defined as enrolled subjects for whom the EkoSonic® Treatment was initiated, i.e. venous access attempted for catheter introduction. The **Safety Subject Set** includes all safety evaluable subjects and will be used for all safety analyses.

Missing data will not be imputed for the primary efficacy and safety analyses. However sensitivity analyses may be performed to assess the robustness of study results with respect to missing data.

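### Visit-by-visit tests of SF-36, PCS and VEINES-QOL change at Days 90, 180 and 365 drop the earlier scores of subjects who left; a repeated-measures model with Baseline as a response would use them

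*Protocol*

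**What the plan says.** Protocol 3.2.1, item 4, makes change in SF-36, PCS and VEINES-QOL a secondary endpoint, measured "from Baseline to 30, 90, 180 and 365 days Post-EkoSonic® Study Treatment Procedure". Section 6.2.1 sets the population and unit: "Analysis for subject specific efficacy measures such as SF-36 will be performed on the Evaluable Subject Set with subject as the analysis unit". It then names the method: "Statistical significance for changes from baseline will be assessed by t-test or a nonparametric test appropriate for the data distribution". Section 6.2.2 sends the secondary endpoints, at all follow-up time points, back to that general methodology.

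On missing data, section 6.1 says "Missing data will not be imputed for the primary efficacy and safety analyses" and adds "However sensitivity analyses may be performed to assess the robustness of study results with respect to missing data". No rule is given for the secondary endpoints. Membership of the subject set requires at least one treated, successfully crossed segment that "had Villalta scores available at both Baseline and 30 days Post-EkoSonic® Treatment visit". Section 4.5 says "Subjects may withdraw from participation at any time during the clinical study". Section 6.2.1 closes with "Further analysis details will be described in the Statistical Analysis Plan".

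**The concern.** Each subject can contribute a Baseline score and up to four later ones. A paired t-test, or its nonparametric counterpart, of the change at one visit needs both Baseline and that visit. A subject who attends Days 30 and 90 and then leaves adds nothing to the Day 180 or Day 365 result, although the earlier scores are on file and are informative about the later ones. The resulting mean is unbiased only if leaving is unrelated to how the subject was doing.

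The study has one arm, so no control group shares the attrition and offsets it. What is at stake is the estimate of how far quality of life has changed by six and twelve months. No success criterion depends on it.

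**Working it through.** **Plan's own figures.** The protocol states no SD, effect, correlation or dropout rate for SF-36 or VEINES-QOL, so there is no planned figure to reproduce. Its numerical claims concern the primary endpoint. For example, the exact binomial probability of at least 35 successes in 70 segments at a true rate of 55% is 0.832, against 0.83 stated in 6.2.4. It plays no part here. Everything below rests on assumed values, with higher scores taken as better.

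**Step 1: direction, by arithmetic.** Let a share π of subjects improve and score D points higher than the rest. Let d_I and d_U be the dropout of improved and unimproved subjects. The improved share among those who remain is

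q = π(1 − d_I) / [π(1 − d_I) + (1 − π)(1 − d_U)],

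and the bias of the mean of those who remain is (q − π)·D. With π = 0.5 and D = 10:

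| d_I | d_U | q | Bias (points) |
|---|---|---|---|
| 0.10 | 0.10 | 0.45/0.90 = 0.500 | 0 |
| 0.10 | 0.30 | 0.45/0.80 = 0.5625 | +0.625 |
| 0.10 | 0.50 | 0.45/0.70 = 0.643 | +1.43 |
| 0.30 | 0.10 | 0.35/0.80 = 0.4375 | −0.625 |

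Size and sign depend entirely on who leaves.

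**Step 2: size over four visits.** Simulation with 70 subjects (a number borrowed from 6.2.4), SD of change 10 and true change 5, with dropout depending on the last observed score. At 26-29% dropout by Day 365, the mean of subjects present is too favourable by about 0.5 to 1.7 points, that is 0.5/5 = 10% to 1.7/5 = 34% of the true change. A likelihood-based repeated-measures estimate from the same data is off by at most 0.08. In a similar run (adjacent-visit correlation 0.6-0.8, odds of leaving multiplied by 1.6-2.7 per SD worse, 21-31% dropout), root mean square error was 1.42-2.11 for the visit-wise mean and 1.28-1.44 for the model.

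**Step 3: how far the result depends on the dropout mechanism.** Two time points, 70 subjects, true Day 365 change of zero, correlation 0.6 between the Day 30 and Day 365 changes, and below-median subjects leaving four times as often. Bias is in SD units at 10%, 20% and 30% dropout:

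| Leaving depends on | Visit-wise mean | Likelihood model |
|---|---|---|
| Nothing relevant | about 0 | about 0 |
| Observed Day 30 change | +0.03, +0.07, +0.12 | about 0 |
| Unseen Day 365 change | +0.05, +0.12, +0.21 | +0.04, +0.08, +0.13 |

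In the second row, false one-sided rejection by the t-test is 4.4%, 7.7% and 12.9%, against a nominal 2.5%. In the third row the model leaves about two thirds of the bias (unrounded at 20% dropout: 0.079/0.123 = 64%).

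**Step 4: how Baseline should enter.** A common form of such a model adjusts for Baseline centred at its sample mean. With equal variances σ² and Baseline-to-follow-up correlation ρ, the true variance of the mean change is 2σ²(1 − ρ)/n. The model reports σ²(1 − ρ²)/n, because it treats the sample Baseline mean as fixed. The ratio of reported to true standard error is √[(1 − ρ²)/(2(1 − ρ))] = √[(1 + ρ)/2].

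- ρ = 0.7: √0.85 = 0.922, so 8% too small.
- ρ = 0.3: √0.65 = 0.806, so 19% too small.

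The large-sample two-sided type I error is 2[1 − Φ(1.96 × ratio)], which gives 7.1% and 11.4%. Simulation at n = 70 gives 6.6% to 11%. With no second arm the error does not cancel. Treating Baseline as one of the responses avoids it.

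**The case against.** The strongest reply is that this belongs in the SAP: 6.2.1 defers further details there, and missing-data handling for a secondary endpoint is a normal SAP matter. Part of that stands. The protocol contains no error or contradiction here, and a SAP could add a missing-data rule. But the protocol does name the test, and a deferral of further details does not withdraw a method already chosen.

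Several stronger readings are tempting, and the document does not support them.

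- **That the plan restricts these analyses to available subjects.** It does not say so. The no-imputation sentence covers only primary efficacy and safety. Using only those present follows from a visit-wise test when no rule brings in other data.
- **That the plan is inconsistent because it uses a mixed model for limbs but not for subjects.** The random subject effect in 6.2.1 handles two segments in one person. Nothing says it models data across visits, so there is no longitudinal method being withheld from SF-36.
- **That the later means will be biased upward.** No dropout rate or pattern is given, and Step 1 shows the sign can reverse. The plan also has safeguards: retention effort (4.5), SF-36 at early termination (4.2.6, 8.7.4) and continued visits after revascularization for symptomatic re-occlusion (4.6). These would limit the bias. They do not remove it: the protocol does not say how an early-termination value enters a scheduled visit's test, and 4.6 does not cover a subject who simply fails to improve and withdraws.
- **That Day 30 is affected in the same way.** The subject set already requires a 30-day Villalta score, so earlier leavers are excluded by definition and no change of test restores them.
- **That all of item 4 is affected.** CEAP and VCSS are scored for each leg (8.7.2, 8.7.3). The point concerns SF-36, PCS and VEINES-QOL.

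It is also fair that a nonparametric option suits skewed scores. Keeping it as a supportive analysis meets that.

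**Conclusion.** The point holds as a modest methodological improvement. The stated test ignores usable earlier data at Days 90, 180 and 365, and it gives too favourable a mean change if subjects doing worse leave more often. The illustration of 0.5 to 1.7 points at Day 365 rests on an assumed SD of 10, a true change of 5, 26-29% dropout and leaving that depends on the last observed score; none of these comes from the protocol. If leaving is unrelated to outcome there is no bias. If it depends on unseen scores, the model reduces the bias only in part. The primary success criterion, the stated probability of success and the futility rule are unaffected.

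**What to change.** In 6.2.1, for the continuous subject-level scores (SF-36, PCS, VEINES-QOL), make the main analysis one mixed model for repeated measures:

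- responses: the scores at Baseline and at 30, 90, 180 and 365 days;
- visit as a categorical factor;
- unstructured within-subject covariance (five time points, so 5 × 6/2 = 15 covariance parameters);
- results: each visit-minus-Baseline contrast with its 95% CI.

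Do not enter Baseline as a mean-centred covariate. Keep the t-test or nonparametric test at each visit as a supportive analysis.

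The cost is a wording change in the protocol and SAP and a little programming; a SAS mixed-model procedure is already named for the segment data. The downside is reliance on missing at random, which is weaker than what the visit-wise test needs but is still an assumption. The change does not bring back subjects left out for lack of a 30-day Villalta score.

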6.2.2 Efficacy

Efficacy analyses will be performed on the Efficacy Segment Set or Efficacy Subject Set as appropriate for the nature of the data.

Primary Clinical Efficacy Analysis:

The 30 day Villalta score change from Baseline will be analyzed as a binary variable for a segment's status as having achieved a ≥ 4 point reduction or not. Study success will be defined by $\geq 50\%$ of the efficacy evaluable segments achieving at least a 4 point reduction. In addition, as a continuous measure, change in Villalta score from Baseline to 30 day Post-EkoSonic® Treatment will also be summarized and analyzed as described above in 6.2.1 General Methodology.

Primary Technical Efficacy Analysis:

The change in blood flow calculated by time to washout in the affected segment from Baseline and Post-EkoSonic® Treatment will be analyzed as a continuous measure. A statistically significant (2-sided $p < 0.05$) improvement in flow rate, i.e. reduction in time to washout, will be considered a success for the study.

Secondary Efficacy Analyses:

For all secondary efficacy endpoints described in Section 3.2.1, i.e. VVI score change from Pre- EkoSonic® Treatment to Post-Treatment, Villalta score change from Baseline to 90, 180, and 365 days, re-occlusion rate up to 365 days, change from Baseline to all follow-up time points for SF-36 QOL and PCS component scores, CEAP classification, and VCSS, occurrences of symptomatic PTS-induced admission to emergency room or unplanned visit

to physician office or hospitalization from post EkoSonic® Treatment up to 365 days thereafter, time from starting initial thrombolytic infusion to discharge from hospital, analyses will be performed as described above in 6.2.1 General Methodology. For symptomatic PTS-induced healthcare utilization, time to event analyses will be performed for days from EkoSonic® Treatment to first occurrence for each of (a) admission to emergency room, (b) unplanned visit to physician office, and (c) hospitalization.

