APPENDIX I: VEINES QOL

APPENDIX J: Adherence to Conservative Treatment Form

A. PROTOCOL SYNOPSIS

Title:	ACCelerated ThrombolySiS for Post-Thrombotic Syndrome Using the EKOS System (ACCESS PTS)
Design:	A prospective, single arm, multi-center study
Brief Device Description:	The EkoSonic® Endovascular System employs high frequency (2-3MHz), low power ultrasound to facilitate the delivery of therapeutic agents to the intravascular treatment site in the peripheral vasculature.
Purpose:	To evaluate the efficacy of ultrasound accelerated thrombolysis using the EkoSonic® Endovascular System with standard infusion of thrombolytic drug for post-thrombotic syndrome and chronic venous occlusion.
Primary Endpoint:	Clinical effectiveness will be evaluated using the Villalta score at Baseline compared to 30 days Post-EkoSonic® Study Treatment Procedure (EkoSonic® Treatment). Success will be defined by 50% of the subjects achieving at least a 4 point reduction in the Villalta score.
Population:	Subjects with lower extremity deep vein thrombosis (who have failed conservative treatment) objectively diagnosed with imaging \geq 6 months; prior persistent DVT at enrollment evaluation; Villalta score \geq 8. Subjects must be \geq 18 years of age and \leq 75 years of age.
Enrollment:	Up to 200 efficacy evaluable subjects, some with bilateral DVTs. Efficacy evaluable DVT limbs are those (1) with Villalta scores available at both Baseline and 30 days Post-EkoSonic® Treatment and (2) the clot in the affected segment was successfully crossed and received EkoSonic® Treatment.
Clinical Site Locations:	Up to 30 centers within the United States.
Time Course:	Enrollment period of up to 12 months with 365 day follow-up. Subject participation is approximately 12 months.

B. STUDY FLOWCHART and SCHEDULE OF EVENTS

ACCESS PTS Schedule of Assessments	Visit 1 (Within 30 days of treatment) Screening/Baseline	Visit 2 Day 0 Pre-EkoSonic® Treatment	Visit 2 Day 0 Post-EkoSonic® Treatment	Discharge	Visit 3 Day 30 ± 7 days	Visit 4 Day 90 ± 10 days	Visit 5 Day 180 ± 14 days	Visit 6 Day 365 ± 14 days	Early Termination
ACTION									
Informed Consent	X								
Demographics	X								
Medical History & Risk Factors	X								
Inclusions/Exclusion Criteria	X								
Pregnancy test	X								
Physical Exam	X								
Duplex Ultrasound	X ¹		X ²		X	X	X	X	X
Adherence to Conservative Therapy Form	X								
Laboratory Tests	X ³	X ⁴	X ²						
Villalta Scale	X				X	X	X	X	X
CEAP Classification	X				X	X	X	X	X

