3.1.1 Primary Clinical Efficacy Endpoint

Clinical efficacy will be evaluated using the Villalta score at Baseline compared to 30 days Post-EkoSonic® Study Treatment Procedure. Study success will be defined by ≥50% of the efficacy evaluable limbs achieving at least a 4 point reduction.

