3.1.2 Primary Technical Efficacy Endpoint

Increase in blood flow calculated by time to washout in the affected segments, measured at Baseline and Post-EkoSonic® Study Treatment Procedure. A statistically significant improvement in flow rate will be considered success.

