4.2.3 EkoSonic® Study Treatment Procedure

The access site is determined by the extent of occlusive disease. When treating a single limb at a time, access via the popliteal vein is reasonable.

Once venous access has been achieved, baseline venography shall be obtained following the guidelines provided in the Venographic Imaging Manual of Operations and Procedures. Confirm presence of chronic DVT causing restrictive flow as well as some degree of flow in the popliteal vein.

Standard catheter and wire techniques are to be utilized to cross the chronic, occlusive clot. Techniques used to cross the occluded segments may include the use of a stiff Glidewire (Terumo Interventional Systems, Somerset, NJ), sharp recanalization, and chronic total occlusion catheters and wires. If a wire can be passed but not the diagnostic catheter, then serial dilatation may be used to create some "working space." Support for better pushability can be obtained by using a graduated system, such as a 4F tibial sheath coaxially through a 6F standard sheath placed through an 8F sheath.

If the occlusion cannot be crossed by the guidewire or EkoSonic® Device or there is severe vessel damage that could be further complicated by thrombolysis, such as perforation, the procedure shall be abandoned and considered a technical failure. The FTC subject shall be followed through 365 days.

Once the occlusion has been successfully crossed, balloon dilatation of the chronic clot shall be performed to create working space and to macerate/crack the hard thrombus. Vessels to be dilated should be sized for appropriate balloon sizing. Example guidelines are: 12-16 mm for IVC, 10-12 mm for iliac veins, 8-10 mm for femoral veins and 6-8 mm for popliteal veins. Cracking the chronic clot may allow for better penetration of alteplase. Once venoplasty has been performed throughout the entire diseased segment, venography imaging shall be obtained prior to placement of the IDDC. Care should be taken to obtain the same images as obtained at baseline venography.

An EkoSonic® IDDC with the treatment zone length selected to cover the entire occlusive segment is placed over the guide wire. The guide wire is then removed and the MSD inserted into the IDDC and luer locked in place. See Appendix C for specific guidance on EkoSonic® Device selection and placement.

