6.2.4 Power Estimation

For the primary efficacy endpoint of change in Villalta score at 30 days from Baseline, study success will be defined by $\geq 50\%$ of the evaluable DVT segments achieving at least a 4 point reduction. Assuming the true underlying proportion of such segments to be 55%, the probability for observing a $\geq 50\%$ success proportion in a study with 70 evaluable independent segments is 0.83. On the other hand, should true underlying success proportion be $<40\%$, e.g. 39%, the probability for observing a $\geq 50\%$ success proportion in 70 independent segments is ≤ 0.04 .

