6.2.5 Interim Clinical Efficacy Futility Analysis

At the time of November 2016 administrative change to the protocol, an interim futility analysis had been performed on the primary clinical efficacy endpoint. The futility stopping criterion was not met and the study continued. It was pre-specified that when data for the primary efficacy endpoint (i.e. change in Villalta score from Baseline to 30 day Post-EkoSonic® Treatment) are available for 35 evaluable subjects segments, an interim futility analysis will be conducted. If 14 or fewer of the 35 segments have achieved a ≥ 4 point reduction for an interim success rate of 40% (1-sided 95% confidence upper limit of 53.9%), early trial termination would be considered due to futility. Should the true success rate be 40% as observed in the interim, the chance of reaching a 50% success rate at full enrollment of 70 evaluable subjects segments (i.e. 21 or more segments in the remaining 35 segments), is ≤ 0.013 . Should the underlying success rate be 53.9%, i.e. the 95% confidence upper limit of the interim success rate, the chance of observing a 50% success rate at full enrollment is still only 0.29. Therefore it is highly unlikely that the trial would meet its efficacy success criterion at full enrollment and early trial termination would be recommended. The negative impact of this futility analysis on the study's power is <0.05 . The study would not stop early due to favorable interim efficacy results; therefore this interim analysis will not incur an alpha cost due to potentially false positive findings.

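### Section 6.2.2 calls a significant washout result a success for the study, while every other study-level success statement rests on the Villalta criterion alone, and no rule says how the two combine

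*Protocol*

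**What the plan says.** **Study success by Villalta.** The synopsis lists one primary endpoint, Villalta at 30 days: "Success will be defined by 50% of the subjects achieving at least a 4 point reduction in the Villalta score". Section 3.1.1 states: "Study success will be defined by ≥50% of the efficacy evaluable limbs achieving at least a 4 point reduction". The clinical paragraph of 6.2.2 and the opening of 6.2.4 repeat the rule for segments. (The change of unit from subjects to limbs to segments is a separate matter.) Section 6.2.4 then gives the chance of meeting the rule with 70 segments: 0.83 at a true rate of 55%, and at most 0.04 at 39%. Section 6.2.5 concludes that after 14 or fewer responders in 35 segments "it is highly unlikely that the trial would meet its efficacy success criterion at full enrollment", with criterion in the singular.

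**Success by washout.** Section 3.1.2 names a second primary endpoint: "Increase in blood flow calculated by time to washout in the affected segments, measured at Baseline and Post-EkoSonic® Study Treatment Procedure". It calls a significant improvement success, without saying of what. Section 6.2.2 goes further: a two-sided p<0.05 "improvement in flow rate, i.e. reduction in time to washout, will be considered a success for the study".

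**What lies between the two washout measurements.** Section 4.0 counts venous access as the start of EkoSonic treatment. Section 4.2.3 places baseline venography directly after access, then requires balloon dilatation of the diseased segment, then a further venogram: "Once venoplasty has been performed throughout the entire diseased segment, venography imaging shall be obtained prior to placement of the IDDC". It adds: "Care should be taken to obtain the same images as obtained at baseline venography". Ultrasound and alteplase follow. Under 4.2.4 there is a venogram after the EkoSonic procedure and another after any adjunctive therapy.

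**The concern.** Section 6.2.2 makes two statements at study level and nothing connects them. A study that misses the Villalta criterion but shows a significant washout change could be reported as successful in the protocol's own words, although Villalta is the only criterion with operating characteristics in the protocol. The figures in 6.2.4 and the futility conclusion in 6.2.5 describe the chance of trial success only if washout is not a route to it and not a further condition.

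What a washout success would mean adds to this. The stated purpose is to evaluate ultrasound-accelerated thrombolysis, but the washout contrast also contains mandatory venoplasty. A significant change is therefore possible without any lytic effect.

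**Working it through.** **Inputs.** From 6.2.4: n = 70 independent segments, success at 35 or more, true rates 39% and 55%. From 6.2.2: washout test at two-sided 0.05. From 6.2.5: 14 of 35 at the interim, so 21 or more of the remaining 35 are needed. Assumed, because the documents give no washout data: a mean shift of d SDs of the paired change, d = 0 to 0.5, and n = 70 for washout as well.

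**Step 1: the protocol's figures.** Let PV = P(X ≥ 35), X ~ Binomial(70, p).
- p = 0.39: PV = 0.0400 (stated: at most 0.04).
- p = 0.55: PV = 0.832 (stated: 0.83).
- Interim, P(X ≥ 21), X ~ Binomial(35, p): 0.0133 at p = 0.40 and 0.291 at p = 0.539 (stated: 0.013 and 0.29).

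All reproduce, and all are for the Villalta rule alone.

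**Step 2: chance that washout is significant in the favourable direction.** For a paired t-test, q = 1 − F(t; 69 df, noncentrality d√70), where F is the noncentral t distribution and t = 1.995 is the 97.5% point on 69 df.

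**Step 3: either result is enough, true Villalta rate 39%.** Whatever the dependence between the endpoints, the chance of a declared success lies between max(PV, q) and min(1, PV + q). The chance that Villalta fails while washout is significant lies between max(0, q − PV) and min(1 − PV, q).

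| Assumed shift (SD) | q | Declared success if either counts | Villalta fails, washout significant |
|---|---|---|---|
| 0 | 0.025 | 0.040-0.065 | 0-0.025 |
| 0.1 | 0.128 | 0.128-0.168 | 0.088-0.128 |
| 0.2 | 0.378 | 0.378-0.418 | 0.338-0.378 |
| 0.3 | 0.697 | 0.697-0.737 | 0.657-0.697 |
| 0.5 | 0.985 | 0.985-1 | 0.945-0.960 |

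**Step 4: both are required, true Villalta rate 55%.** The chance of success lies between max(0, PV + q − 1) and min(PV, q).
- d = 0.3: 0.832 + 0.697 − 1 = 0.529, up to 0.697 (0.832 × 0.697 = 0.58 under independence).
- d = 0.5: 0.832 + 0.985 − 1 = 0.817, up to 0.832.

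The stated 0.83 is then a ceiling.

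**Step 5: sensitivity.**
- *Bilateral limbs.* With a fraction f of subjects bilateral, the design effect is 1 + [(1 + 3f)/(1 + f) − 1] × ICC. Assuming f = 0.2 and ICC = 0.5, it is 1 + 0.333 × 0.5 = 1.167, and the effective n is 70/1.167 = 60. Then q = 0.115, 0.331, 0.628 and 0.968 at 0.1, 0.2, 0.3 and 0.5 SD, modestly lower than in the table.
- *Larger enrolment.* Section 4.0 allows up to 200 evaluable subjects. With 200 segments the Villalta rule (100 or more) passes a 39% rate with probability 0.001, while washout alone is significant with probability 0.80 at 0.2 SD. The two rules move further apart as enrolment grows.

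**The case against.** **The washout sentence may mean only technical success.** It stands under the technical-analysis heading, it echoes the unqualified success in 3.1.2, and the Villalta sentences alone use defining language. Section 6.2.5 is headed as a clinical efficacy analysis. No text says that either result is enough, and the SAP could hold a combining rule. This stands in part: a reader might infer that the protocol allows study success on washout alone, but the text is silent between one and both. The silence is the defect, because the protocol itself has put both statements at study level.

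**The larger probabilities are not false positives.** This stands. With no washout change the range is only 0.040-0.065. The higher figures need a real whole-procedure change, which the technical endpoint would detect correctly. They show how often a study with a poor Villalta response could be called successful, not an inflated error rate for washout. The 0.04 in 6.2.4, read as a statement about Villalta, stays true.

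**Venoplasty is part of the treatment.** This also stands. Because 4.0 and 4.2.3 place it inside the study treatment procedure that the endpoint spans, a reader who concludes that the washout contrast is wrongly built goes too far. It is a coherent whole-procedure measure with a limit on attribution, and Villalta shares that limit in a single-arm design.

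**The imaging method for washout is not named.** This stands. Venography is an inference, although the baseline and post-procedure duplex pair also spans venoplasty. Whether washout can be read on the post-venoplasty images is unknown.

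**Conclusion.** The inconsistency is real and should be corrected. Section 6.2.2 gives washout study-level standing that the synopsis, 3.1.1, 6.2.4 and 6.2.5 do not, and no combining rule is stated. Of the three readings, only washout as technical success leaves the figures of 6.2.4 and the futility conclusion of 6.2.5 intact as statements about study success.

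The size depends on the reading. If either result counts, a declared success at a true 39% Villalta response has probability 0.040-0.065 with no washout change, 0.38-0.42 at 0.2 SD and 0.70-0.74 at 0.3 SD. If both are needed, power is at most 0.83, and 0.53-0.70 at 0.3 SD. The shifts and the use of n = 70 for washout are assumptions; the bounds hold for any dependence between the endpoints. The documents do not support saying that the protocol adopts an either-or rule, that the type I error is 70%, or that the washout endpoint is invalid.

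**What to change.** 1. In 6.2.2 and 3.1.2, replace the washout success wording with success on the technical endpoint. State once that study success is defined only by the Villalta criterion, and list washout in the synopsis as the technical endpoint. This costs wording only. Although it follows the interim look reported in 6.2.5, it removes a possible claim and adds none. An explicit rule requiring both would also settle the text, but 6.2.4 and 6.2.5 would then have to be recalculated with a washout assumption.

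2. Describe washout as a whole-procedure result that includes mandatory venoplasty and so cannot by itself show a lytic effect. Name the imaging method and the image that closes the contrast, before or after adjunctive treatment. This again costs wording only.

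3. Optional: if washout can be read on the already required post-venoplasty, pre-IDDC venogram, report the change from there to the post-EkoSonic, pre-adjunctive venogram as a supportive estimate with a 95% CI and no success rule. It would reflect ultrasound and alteplase together and is not a clean separation, since 4.2.3 itself suggests that dilatation may help alteplase penetrate. The cost is extra image reading and a probably smaller effect. Because it would be added after the interim look, it should replace no endpoint.
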